 - Uncontrolled angina pectoris within 6 months prior to screening.
 - New York Heart Association (NYHA) Class 3 or 4 congestive heart failure.
 - Left ventricular ejection fraction (LVEF) $\leq 45\%$ or institutional lower limit of normal.
 - Uncontrolled hypertension.
 - Complete left or right bundle branch block.
13. Active infection not well controlled by antibacterial, antifungal, and/or antiviral therapy.
14. Known infection with human immunodeficiency virus, or active hepatitis B or C, or other active clinically relevant liver disease.
15. Unwillingness to receive infusion of blood products according to the protocol.
16. In a man whose sexual partner is a woman of childbearing potential, unwillingness or inability of the man or woman to use a highly effective contraceptive method for the entire study treatment period and for at least 3 months after study treatment completion.
- Male subjects must not freeze or donate sperm starting at Screening and throughout the study period and 105 days after the final study drug administration.
17. In a heterosexually active woman of childbearing potential, unwillingness or inability to use a highly effective contraceptive method for the entire study treatment period and for at least 3 months after study treatment completion. Additionally, for women randomized to chemotherapy, unwillingness to adhere to the restrictions in the respective locally established guidelines and local approved label (prescribing information, Summary of Product Characteristics, or US product insert) from the manufacturer and the Patient Information Leaflet (package insert) as instructed by the Investigator.
- Women are not regarded as of childbearing potential if they are post-menopausal (at least 2 years without menses) or are surgically sterile (at least 1 month before study).
 - Highly effective contraception methods include: hormonal methods associated with inhibition of ovulation, intra-uterine device; surgical sterilization (including partner's vasectomy) or sexual abstinence if this is the preferred and usual lifestyle of the subject.
 - Female subjects must not donate or retrieve, for their own use, ova from the time of Screening and throughout the study treatment period, and for 12 weeks after the

final study drug administration.

18. Pregnancy

19. Female subjects must agree not to breastfeed from the time of Screening and throughout the study period, and for 25 days after the final study drug administration.

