 - Uncontrolled angina pectoris within 6 months prior to screening
 - New York Heart Association (NYHA) Class 3 or 4 congestive heart failure
 - Left ventricular ejection fraction (LVEF) \leq 45% or institutional lower limit of normal
 - Uncontrolled hypertension
 - Complete left or right bundle branch block
13. Active infection not well controlled by antibacterial, antifungal, and/or antiviral therapy
14. Known infection with human immunodeficiency virus, or active hepatitis B or C, or other active clinically relevant liver disease
15. Unwillingness to receive infusion of blood products according to the protocol
16. In a man whose sexual partner is a woman of childbearing potential, unwillingness or inability of the man or woman to use a highly effective contraceptive method for the entire study treatment period and for at least 3 months after study treatment completion
 - Male subjects must not freeze or donate sperm starting at Screening and throughout the study period, and 105 days after the final study drug administration.
17. In a heterosexually active woman of childbearing potential, unwillingness or inability to use a highly effective contraceptive method for the entire study treatment period and for at least 3 months after study treatment completion. Additionally, for women

randomized to chemotherapy, unwillingness to adhere to the restrictions respective locally established guidelines and local approved label (prescribing information, Summary of Product Characteristics, or US product insert) from the manufacturer and the Patient Information Leaflet (package insert) as instructed by the Investigator.

- Women are not regarded as of childbearing potential if they are post-menopausal (at least 2 years without menses) or are surgically sterile (at least 1 month before study).
- Highly effective contraception methods include: hormonal methods associated with inhibition of ovulation, intra-uterine device; surgical sterilization (including partner's vasectomy) or sexual abstinence if this is the preferred and usual lifestyle of the subject.
- Female subjects must not donate or retrieve, for their own use, ova from the time of Screening and throughout the study treatment period, and for 12 weeks after the final study drug administration.

18. Pregnancy

19. Female subjects must agree not to breastfeed from the time of Screening and throughout the study period, and for 25 days after the final study drug administration.

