5.4.4.2. Exclusion Criteria for Cross-Over

Candidates will be excluded from cross-over to quizartinib if any of the following criteria are met at Screening or other specified time point:

1. QTcF interval > 450 msec (average of triplicate determinations.)
2. Subject has bradycardia of less than 50 BPM (as determined by central reading).
3. Uncontrolled hypertension.
4. Active infection not well controlled by antibacterial, antifungal, and/or antiviral therapy.
5. In a man whose sexual partner is a woman of childbearing potential, unwillingness or inability of the man or woman to continue to use a highly effective contraceptive method for the entire study treatment period and for at least 3 months after study treatment completion:
 - Male subjects must not freeze or donate sperm starting at Screening and throughout the study period, and 105 days after the final study drug administration.
6. In a heterosexually active woman of childbearing potential, unwillingness or inability to continue to use a highly effective contraceptive method for the entire study treatment period and for at least 3 months after study treatment completion.
 - Women are not regarded as of childbearing potential if they are post-menopausal (at least 2 years without menses) or are surgically sterile (at least 1 month before study).
 - Highly effective contraception methods include: hormonal methods associated with inhibition of ovulation, intra-uterine device; surgical sterilization (including partner's vasectomy); or sexual abstinence if this is the preferred and usual lifestyle of the subject.
 - Female subjects must not donate or retrieve, for their own use, ova from the time of screening and throughout the study treatment period, and for 12 weeks after study treatment completion.
7. Pregnancy
8. Female subjects must agree not to breastfeed from the time of Screening and throughout the study period, and for 25 days after the final study drug administration.
9. For subjects in the UK only: Refusal of permission to allow the subject's General Practitioner to be notified of his or her participation in the study.

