6. STUDY VISITS AND ACTIVITIES

6.1. Acceptable Windows for Protocol Assessments and Follow-up Visits

Unless otherwise specified in the enrollment criteria, Schedule of Activities table, and in other sections of the protocol, Table 7 serves as a general guideline for acceptable windows within which assessments and procedures are conducted and when study visits are scheduled.

Table 7 Windows for Performing Assessments and Scheduling Follow-Up Visits

PK Assessments	
Time Points	Acceptable Window
Predose	< 60 minutes prior to study drug administration
Start of study drug to < 1 hour postdose	± 5 minutes
1 hour postdose to ≤ 6 hours postdose	± 30 minutes, but the PK samples should be taken as close to the protocol stipulated times as possible
24 hours postdose	□ 3 hour prior to next dose
Study Visits	
Visit/Day	Acceptable Window
Pretreatment Visit	Scheduled within 14 days prior to randomization ^a
Cycle 1 Day 1 and 2	No window applies
Cycle 1 Day 8	± 1 day
Cycle 1 Days 15 and 16	± 1 day for Day 15; Day 16 must be the day after Day 15
Cycle 2 Day 1	± 3 days ^b
Cycle 2 Day 15	± 1 day
Cycle 3 Day 1	± 3 days ^b
Ongoing Visits	Every 28 days (± 3 days) ^b ; and Day 15 of each cycle (± 1 day)
Early Termination or End of Study	7 ± 1 day from date of final dose of quizartinib or site's knowledge of reason for study discontinuation

a Bone marrow assessments at Screening can be done within 14 days of randomization; bone marrow examinations outside this window may be acceptable if agreed by the Medical Monitor.

b The ± 3 day window for Cycle 2 Day 1 and Day 1 of ALL cycles thereafter allows scheduling of necessary assessments (including bone marrow aspirates and/or biopsies), obtaining test results, preparing study drug and dispensing for those subjects receiving subsequent cycles of therapy (refer to Schedule of Activities and its footnotes for exceptions). Despite this window, every effort must be made such that there are no dosing schedule interruptions for subjects on this continuous dosing regimen.

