6.2.5. Schedule of Activities and Assessments after Treatment

6.2.5.1. End of Treatment Visit

The end of treatment visit should occur within 7 days of the last dose of quizartinib or correspond to Day 29 for the last cycle of salvage chemotherapy. For MEC or FLAG-IDA the end of treatment visit would be Cycle 1 Day 29 or Cycle 2 Day 29.

For subjects on quizartinib who discontinue treatment with the objective of proceeding to HSCT, a quizartinib end of treatment visit should occur. Additionally subjects moving onto HSCT must have a 30 Day Follow-up phone contact. Subsequently, if subject undergoes HSCT, restarts quizartinib and later discontinues treatment, a post-HSCT end of treatment visit should also occur.

The following activities will take place during this visit:

- Physical examination
- Vital sign determinations
- ECOG performance status evaluation
- Review of concomitant medications
- Serum pregnancy testing for women of childbearing potential
- 12-lead ECG (triplicate)
- Collection of samples for clinical laboratory tests (hematology, chemistry, and urinalysis)
- Bone marrow aspiration and biopsy for local response determination are preferred, but biopsy may be omitted if the aspirate is considered to be adequate. For subjects receiving chemotherapy response assessment may be at Day 29 \pm 14 days.
- Collection of specimen for exploratory assessment of FLT3 mutations using bone marrow or whole blood will be performed (for subjects in the quizartinib arm only).

- If consent is provided, collection of blood (Pax gene RNA) for pharmacogenomic and proteomic determinations
- AE/SAE evaluation
- Review medication and assessment of compliance

Note: Physical examination, vital sign determinations, ECOG performance status determination, and clinical laboratory tests need not be repeated if they were performed at a regularly scheduled visit within 3 days of the end of treatment visit.

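### Men on quizartinib: the 3-month contraception minimum runs from an undefined completion of treatment and can end 13 to 16 days before the protocol's own 105-day sperm limit

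*Combined protocol and SAP*

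**What the plan says.** Section 5.4.2, exclusion 16, gives men two time limits.

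- **Contraception.** A man with a partner of childbearing potential may enter only if it is acceptable and possible for him or the "woman to use a highly effective contraceptive method for the entire study treatment period and for at least 3 months after study treatment completion".
- **Sperm.** The sub-bullet reads: "Male subjects must not freeze or donate sperm starting at Screening and throughout the study period, and 105 days after the final study drug administration".

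The synopsis carries the same pair, with the sperm bar running "throughout the study period and 105 days after the final study drug administration". Cross-over exclusion 5 in Section 5.4.4.2 again requires men and their partners "to continue to use a highly effective contraceptive method for the entire study treatment period and for at least 3 months after study treatment completion", followed by the same 105-day bar.

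The contraception limit is counted from completion of study treatment, which the protocol does not define. The sperm limit is counted from the final dose. No reason is given for the two lengths or the two starting points.

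The rules for women give a hint about meaning. In Section 5.4.2, item 17, the limit covers "ova from the time of Screening and throughout the study treatment period, and for 12 weeks after the final study drug administration". In Section 5.4.4.2, item 6, it covers "ova from the time of screening and throughout the study treatment period, and for 12 weeks after study treatment completion". The same 12 weeks is counted from the final dose in one place and from completion in the other.

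**The concern.** Both male rules limit the use of sperm after exposure to the drug. If completion means the last dose, a man who follows the protocol exactly may stop contraception while the protocol still bars him from donating or freezing sperm. Nothing in the text explains why the shorter period should apply to conception with a partner.

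The undefined starting point is a second weakness, because two sites could give two men different end dates and both would be following the text.

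What is at stake is partner and fetal safety. Sample size, type I error and the efficacy analyses are untouched.

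**Working it through.** The plan states no figure to reproduce; this is calendar arithmetic.

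**Inputs**
- Contraception minimum: 3 months after completion (synopsis item 16; Section 5.4.2 item 16; Section 5.4.4.2 item 5). In days this is 89 (1 February to 1 May in a common year: 28 + 31 + 30) to 92 (1 July to 1 October: 31 + 31 + 30).
- Sperm limit: day 105 after the final dose (same items).
- Candidate dates for completion, in days after the last quizartinib dose: the last dose itself (0); the end-of-treatment visit (0 to 7, since Section 6.2.5.1 says "The end of treatment visit should occur within 7 days of the last dose of quizartinib"); the 30-day follow-up (30, Sections 5.1.3 and 6.2.5.3).

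**Formula**

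Shortfall = 105 − (days from last dose to completion + length of 3 months). A positive value means that the contraception minimum ends before the 105-day limit.

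| Completion means | Smallest | Largest | Shortfall |
|---|---|---|---|
| Last dose | 105 − (0 + 92) = 13 | 105 − (0 + 89) = 16 | 13 to 16 days |
| End-of-treatment visit | 105 − (7 + 92) = 6 | 105 − (0 + 89) = 16 | 6 to 16 days |
| 30-day follow-up | 105 − (30 + 92) = −17 | 105 − (30 + 89) = −14 | none; contraception runs 14 to 17 days longer |

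**Break-even.** The shortfall is zero when completion falls 105 − 92 = 13 to 105 − 89 = 16 days after the last dose. From day 16 onward there is never a gap.

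**Share covered on the last-dose reading.** 89/105 = 85% to 92/105 = 88% of the sperm limit.

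**Comparison with the rules for women.** The ova limit is 12 × 7 = 84 days. On the last-dose reading, women's contraception minimum outlasts it by 89 − 84 = 5 to 92 − 84 = 8 days. For men the order is reversed.

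**After the change.** If the minimum is the later of 3 months after completion and day 105 after the final quizartinib dose, it can never end before day 105. The added contraception is 13 to 16 days on the last-dose reading, 6 to 16 on the end-of-treatment reading, and none on the 30-day reading.

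**The case against.** The strongest reply is that nothing conflicts. Donating or freezing sperm and using contraception with a partner are different acts, a man can comply with both rules, and the 3 months is a minimum. That stands: a reader might infer a contradiction, and the text does not contain one. But the minimum is all that a compliant man is asked to meet, so its length still matters.

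A second reply is that little drug can remain. Section 3.3 gives an effective half-life of about 3 days for quizartinib and its metabolite, so day 89 is about 89/3 ≈ 30 half-lives after the last dose. This weakens any argument from residual drug. It does not explain why the protocol chose 105 days for sperm, and the documents give no other basis for that figure.

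Four stronger readings are tempting and are not supported.

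- **That the gap applies to all men.** For chemotherapy, the end-of-treatment visit is Day 29 of the last cycle. Nominal last doses on Day 10 (LoDAC), Day 6 (FLAG-IDA) and Day 5 (MEC) put it 29 − 10 = 19, 29 − 6 = 23 and 29 − 5 = 24 days later, past break-even. Nor does the text say whether commercial chemotherapy counts as study drug here. The point is limited to quizartinib.
- **That the early termination visit gives another fixed range.** Table 7 also lets that visit be timed from the site's knowledge of the reason for discontinuation, and Section 6.2.6 counts from the withdrawal decision. It has no fixed distance from the last dose, so no range follows.
- **That 105 days is three months plus a washout.** Five half-lives, the washout that inclusion 8 uses for non-cytotoxic agents, would be about 15 days, and 105 − 15 = 90. The numbers fit, but the protocol states no such derivation.
- **That aligning to 105 days makes the two rules identical.** The sperm bar also runs throughout the study period, a term left undefined. If that includes long-term follow-up, the bar could last longer still. Only the 105-day part is compared here.

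**Conclusion.** The mismatch is real for men on quizartinib and low in priority. The contraception minimum ends 13 to 16 days before the 105-day sperm limit if completion means the last dose, and 6 to 16 days before it if completion means the end-of-treatment visit. There is no gap if completion falls 16 or more days after the last dose.

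The conclusion rests on reading 3 months as calendar months and on the absence of a definition of completion. The interchangeable wording of the ova limit favours the last-dose reading without settling it. The reason for the 105 days and the number of men with a partner of childbearing potential are not in the documents, so neither the hazard nor the number exposed can be estimated. This is a cheap improvement to a safety rule.

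**What to change.** In synopsis exclusion 16, Section 5.4.2 item 16 and Section 5.4.4.2 item 5, require contraception for men on quizartinib, and their partners, until the later of (a) 3 months after completion of study treatment and (b) 105 days after the final quizartinib dose. Keeping (a) means that nobody's period is shortened. Adding (b) matches the 105-day part of the sperm restriction whatever completion is taken to mean.

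The cost is amendment and consent wording, with ethics approval under Section 14.3 at a study planned for about 150 centers, and up to 13 to 16 more days of contraception for the men concerned. No visit, test or analysis changes. Given the low priority, the wording could be carried in the next amendment made for another reason.

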5.4.3. Inclusion of Women, Minorities, and Other Underrepresented Populations

This study is open to all subpopulations of subjects who fulfill eligibility criteria.

5.4.4. Eligibility to Cross-Over to Quizartinib from Salvage Chemotherapy

5.4.4.1. Inclusion Criteria for Cross-Over

To be able to cross-over to quizartinib therapy from salvage chemotherapy, candidates must meet the following criteria at screening or other specified time point:

1. Provision of written informed consent approved by the IRB or IEC with privacy language in accordance with national regulations (eg, HIPAA authorization for US sites) prior to any study-related procedures, including withdrawal of prohibited medications if applicable.
2. ECOG performance score 0-2.
3. Serum creatinine $\leq 1.5 \times \text{ULN}$, or glomerular filtration rate $> 25 \text{ mL/min}$, as calculated with the Cockcroft-Gault formula.
4. Serum potassium, magnesium, and calcium (serum calcium corrected for hypoalbuminemia) within institutional normal limits. Subjects with electrolytes outside

the normal range will be eligible if these values are corrected upon retesting following any necessary supplementation.

5. Total serum bilirubin $\leq 1.5 \times \text{ULN}$.
6. Serum AST and/or ALT $\leq 2.5 \times \text{ULN}$.

5.4.4.2. Exclusion Criteria for Cross-Over

Candidates will be excluded from cross-over to quizartinib if any of the following criteria are met at Screening or other specified time point:

1. QTcF interval > 450 msec (average of triplicate determinations.)
2. Subject has bradycardia of less than 50 BPM (as determined by central reading).
3. Uncontrolled hypertension.
4. Active infection not well controlled by antibacterial, antifungal, and/or antiviral therapy.
5. In a man whose sexual partner is a woman of childbearing potential, unwillingness or inability of the man or woman to continue to use a highly effective contraceptive method for the entire study treatment period and for at least 3 months after study treatment completion:
 - Male subjects must not freeze or donate sperm starting at Screening and throughout the study period, and 105 days after the final study drug administration.
6. In a heterosexually active woman of childbearing potential, unwillingness or inability to continue to use a highly effective contraceptive method for the entire study treatment period and for at least 3 months after study treatment completion.
 - Women are not regarded as of childbearing potential if they are post-menopausal (at least 2 years without menses) or are surgically sterile (at least 1 month before study).
 - Highly effective contraception methods include: hormonal methods associated with inhibition of ovulation, intra-uterine device; surgical sterilization (including partner's vasectomy); or sexual abstinence if this is the preferred and usual lifestyle of the subject.
 - Female subjects must not donate or retrieve, for their own use, ova from the time of screening and throughout the study treatment period, and for 12 weeks after study treatment completion.
7. Pregnancy
8. Female subjects must agree not to breastfeed from the time of Screening and throughout the study period, and for 25 days after the final study drug administration.
9. For subjects in the UK only: Refusal of permission to allow the subject's General Practitioner to be notified of his or her participation in the study.

5.4.5. Subject Withdrawal Criteria

Subjects are free to withdraw consent and discontinue participation in the study at any time and without prejudice to future treatment. A subject's participation in the study may be discontinued

at any time at the Investigator's discretion. Justifiable reasons for a subject to be withdrawn from the study include:

- Noncompliance with study procedures or study site rules, including failure to take study medication or to appear at 1 or more study visits
- Use of any prohibited concomitant medication, supplement, food, or beverage without prior approval by the Investigator and Sponsor
- Erroneous inclusion of the subject in the study
- Major protocol deviation presenting an unnecessary risk to the subject's health
- Lost to follow-up

Study treatments must be withdrawn for any of the following reasons:

- Intolerable AE related to study treatment, including Grade 4 QTcF prolongation
- Resting LVEF <45%
- Pregnancy
- Termination of the study by the Sponsor
- Withdrawal of informed consent for any reason
- Any clinical AE or abnormal laboratory test result indicating, in the Investigator's opinion, that continued study drug dosing is not in the subject's best interest

The reason for subject withdrawal should be recorded on the appropriate case report form (CRF).

Only subjects who refuse all of the following methods of follow-up will be considered to have withdrawn consent from study participation:

- Participation in the 30-Day Follow-up Visit per protocol, either in clinic or by telephone;
- Study personnel contacting the subject by telephone (may be quarterly, bi-annually, annually, or only at end of study);
- Study personnel contacting an alternative person (eg, family member, spouse, partner, legal representative, physician, or other healthcare provider);
- Study personnel accessing and reviewing the subject's medical information from alternative sources (eg, doctor's notes, hospital records).

If the subject refuses all of the above methods of follow-up, the Investigator should personally speak to the subject to ensure the subject understands all of the potential methods of follow-up. If the subject continues to refuse all potential methods of follow-up, the Investigator will document this as a withdrawal of consent in the medical record and in the CRF.

For subjects who withdraw consent as define above, study personnel will use local, regional, and national public records (in accordance with local laws) to monitor vital status.

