5.4.2. Exclusion Criteria

Candidates will be excluded from study entry if any of the following criteria are met at screening or other specified time point:

1. Acute promyelocytic leukemia (AML subtype M3)
2. AML secondary to prior chemotherapy for other neoplasms, except AML secondary to prior MDS
3. History of another malignancy, unless the candidate has been disease-free for at least 5 years
 - Candidates with treated non-melanoma skin cancer, carcinoma in situ, or cervical intraepithelial neoplasia are eligible regardless of the time spent disease-free, if they have completed definitive treatment
 - Candidates with organ-confined prostate cancer, with no evidence of recurrent or progressive disease, are eligible if hormonal therapy has been begun, or if the tumor has been surgically removed or treated with definitive radiotherapy
4. Persistent, clinically significant $>$ Grade 1 non-hematologic toxicity from prior AML therapy
5. Clinically significant GVHD or GVHD requiring initiation of treatment or treatment escalation within 21 days, and/or $>$ Grade 1 persistent or clinically significant non-hematologic toxicity related to HSCT
6. History of or current, central nervous system involvement with AML
7. Clinically significant coagulation abnormality, such as disseminated intravascular coagulation
8. Prior treatment with quizartinib or participated in a prior quizartinib study

9. Prior treatment with a FLT3 targeted therapy including sorafenib or investigational FLT3 inhibitors (not including the multi-kinase inhibitor, midostaurin)
10. Major surgery within 4 weeks prior to screening
11. Radiation therapy within 4 weeks prior to screening
12. Uncontrolled or significant cardiovascular disease, including:
 - QTcF interval >450 msec (average of triplicate determinations)
 - Subject has bradycardia of less than 50 BPM (as determined by central reading) unless the subject has a pacemaker
 - Diagnosed or suspected long QT syndrome, or known family history of long QT syndrome
 - History of clinically relevant ventricular arrhythmias, such as ventricular tachycardia, ventricular fibrillation, or torsade de pointes
 - History of second or third degree heart block. Candidates with a history of heart block may be eligible if they currently have pacemakers, and have no history of fainting or clinically relevant arrhythmia with pacemakers.
 - Myocardial infarction within 6 months prior to screening

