20. Medical condition, serious intercurrent illness, or other circumstance that, in the Investigator's judgment, could jeopardize the candidate's safety as a study subject, or that could interfere with study objectives.

21. For subjects in the UK only: Refusal of permission to allow the subject's General Practitioner to be notified of their participation in the study.

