5.6.4.4. Quizartinib Dose Reduction Rules and Definitions

The dose of quizartinib will be reduced stepwise from 60 mg/day to 30 mg/day or from 30 mg/day to 20 mg/day, based on the following criteria:

QTcF (QT interval corrected with Fridericia's formula) Prolongation

- Grade 2 (QTcF average of triplicate readings > 480 msec)
 - The dose will be reduced without interruption.
 - If 20 mg/day is the current dose, dosing will be interrupted for up to 14 days. If QTcF returns to within 30 msec of baseline or ≤ 450 msec within 14 days, treatment may be resumed at 20 mg/day.
- Grade 3 (QTcF average of triplicate readings > 500 msec)
 - Dosing will be interrupted for up to 14 days. If QTcF returns to within 30 msec of baseline or ≤ 450 msec within 14 days, treatment may be resumed at a reduced dose.
 - If 20 mg/day is the current dose, dosing will be interrupted for up to 14 days. If QTcF returns to within 30 msec of baseline or ≤ 450 msec within 14 days, treatment may be resumed at 20 mg/day. If Grade 3 event returns, treatment will be discontinued.
- Grade 4 (QTcF >500 msec or >60 msec change from baseline, and Torsade de pointes or polymorphic ventricular tachycardia or signs/symptoms of serious arrhythmia)
 - Treatment will be discontinued.

See Section 8.5 for clinical guidelines for the management of QT prolongation.

Non-hematologic Toxicity

Grade 3 or 4 related to quizartinib and persisting >48 hours without improvement to \leq Grade 2.

- Dosing will be interrupted for up to 14 days.

- If toxicity improves to \leq Grade 1 within 14 days, treatment may be resumed at the reduced dose.

Myelosuppression

In a subject with CRp or CRi, the dose may be reduced at the Investigator's discretion if:

- The subject has been treated for a minimum of 2 cycles.
- Platelet count is $<100 \times 10^9/L$ and ANC is $\leq 1000 \times 10^9/L$.
- Marrow blast count is $<5\%$.
- There is no evidence of extramedullary disease.

Initiation of concomitant treatment with a strong CYP3A4 inhibitor is identified in [Appendix 1: List of Potential QT Prolonging Drugs, CYP3A4 Inhibitors/Inducers, and P-glycoprotein Inhibitors/Inducers](#).

The dose will be reduced one level (60 mg to 30 mg or 30 mg to 20 mg) when treatment with a strong CYP3A4 inhibitor is initiated.

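### The cross-over criteria set no LVEF limit although a resting LVEF below 45% is a mandatory stop, and they omit new ventricular arrhythmia and the investigator-judgment exclusion

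*Combined protocol and SAP*

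**What the plan says.** Section 5.1 lets the sponsor offer quizartinib to control subjects after a positive interim or final analysis and database lock, if safety parameters in the eligibility criteria are met. It points to Section 5.4 as a whole.

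The dedicated cross-over criteria are in 5.4.4. The inclusion list (5.4.4.1) has six items and keeps the electrolyte requirement: "Serum potassium, magnesium, and calcium (serum calcium corrected for hypoalbuminemia) within institutional normal limits". The exclusion list (5.4.4.2) has nine items and opens with: "Candidates will be excluded from cross-over to quizartinib if any of the following criteria are met at Screening or other specified time point". Its cardiovascular items are QTcF above 450 msec, bradycardia below 50 BPM and uncontrolled hypertension.

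At study entry, 5.4.2 item 12 also excludes an LVEF at or below "45% or institutional lower limit of normal", and: "History of clinically relevant ventricular arrhythmias, such as ventricular tachycardia, ventricular fibrillation, or torsade de pointes". Item 20 adds a general bar: "Medical condition, serious intercurrent illness, or other circumstance that, in the Investigator's judgment, could jeopardize the candidate's safety as a study subject".

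Section 5.4.5 lists the mandatory reasons to withdraw study treatment. They include "Resting LVEF <45" percent and "Intolerable AE related to study treatment, including Grade 4 QTcF prolongation". Section 5.6.4.4 defines Grade 4 as a QTcF change "and Torsade de pointes or polymorphic ventricular tachycardia or signs/symptoms of serious arrhythmia".

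**The concern.** A start rule should not admit a subject whom the stop rule must take off at once. As listed, the cross-over criteria do so for LVEF: a known value below 45% is no bar to starting, yet withdrawal is mandatory at that value.

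Cross-over also gives a drug that section 8.5 says prolongs QT to subjects who have since had salvage chemotherapy. An arrhythmia that arose after randomization could not have been caught by entry screening, and 5.4.4.2 neither names it nor gives the investigator a general ground for exclusion. At stake is consistent, safe handling of a small number of control subjects across about 150 centers.

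**Working it through.** The plan gives no figure on this point. The check is a comparison of the lists, followed by a ceiling on how many subjects could be concerned.

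**Lists side by side.** Item 12 of 5.4.2 has 11 cardiac bars.

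| Entry bar (5.4.2 item 12) | In 5.4.4.2? | Named stop in 5.4.5? |
|---|---|---|
| QTcF, bradycardia, hypertension (3) | Yes | Grade 4 QTcF only |
| LVEF (1) | No | Yes, below 45% |
| Ventricular arrhythmia (1) | No | Only as Grade 4 QTcF |
| Long QT syndrome (1) | No; screened at entry | No |
| Heart block, MI, angina, NYHA 3-4, bundle branch block (5) | No | No |

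The count is 3 + 1 + 1 + 1 + 5 = 11, so 3 are kept and 8 are not. LVEF is the one omitted bar that is itself a named mandatory stop. Item 20 has no counterpart in 5.4.4.2.

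**Does 5.1 close the gap?** Section 5.4 contains both the entry list and the cross-over list. If 5.4.4 alone governs, the LVEF gap is real. If 5.4.2 also applies, its LVEF bar applies, but so might entry inclusion 8 (two weeks off cytotoxic agents), which contradicts the no-washout rule in 6.2.5.2. So the entry criteria cannot carry over in full, and 5.1 does not say which do.

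**When would an LVEF line act?** Table 5 footnote e schedules a repeat MUGA or ECHO only for FLAG-IDA, before Cycle 2. For MEC and LoDAC the only scheduled value is the screening one, which had to exceed 45%. The line therefore acts on the FLAG-IDA pre-Cycle-2 scan or on an unscheduled scan.

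**Ceiling on candidates.** Inputs from section 13.3: 363 subjects (242 quizartinib, 121 control), median survival 6.0 and 3.9 months, accrual over R = 17 months or R = 363/19.2 = 18.9 months. Assumed: uniform accrual, exponential survival, and a drop-out hazard η of 0 or 0.0158 per month, because the plan's 10% has no time unit. The higher value means that 0.0158/(0.0158 + 0.1777) = 8% of controls and 0.0158/(0.0158 + 0.1155) = 12% of quizartinib subjects eventually drop out before death.

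Hazards: λ = ln 2/3.9 = 0.1777 (control) and ln 2/6.0 = 0.1155 (quizartinib); h = λ + η; a = min(t, R).

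- Deaths by month t, per arm of size n: (n/R)(λ/h){a − [exp(−h(t−a)) − exp(−ht)]/h}. Sum the arms and solve for 140 and 280.
- Controls alive and in follow-up at t: (121/R)[exp(−h(t−a)) − exp(−ht)]/h.
- After a lag L to lock: multiply by exp(−hL).

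Example (R = 17, η = 0): 140 deaths fall at month 12.67. Controls alive = (121/17)(1 − exp(−0.1777 × 12.67))/0.1777 = 35.8. After 1 month, 35.8 × 0.837 = 30.0; after 3 months, 35.8 × 0.587 = 21.0.

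| Cut-off | Month | Alive at cut-off | 1-month lag | 3-month lag |
|---|---|---|---|---|
| 140 deaths | 12.7 to 14.0 | 30.9 to 35.8 | about 25 to 30 | 17.3 to 21.0 |
| 280 deaths | 21.2 to 25.1 | 9.6 to 18.3 | 7.9 to 15.3 | 5.4 to 10.7 |

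The lag is assumed. Section 5.3 puts the 280th death near month 36. Stretching accrual to meet that date (R of 33.3 to 36.9 months) gives 11.1 to 18.4 controls alive at the final cut-off, so the order of size does not change. ECOG, laboratory, infection and consent requirements are not applied.

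**The case against.** The best reply has four parts.

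*The stop rule corrects the problem.* A compliant site that knows the LVEF is 40% has no basis for continued dosing. That is fair, and it limits the harm. The text still lets the subject start.

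*General judgment is already available.* Section 5.4.5 allows participation to be discontinued at the investigator's discretion at any time, and requires withdrawal when a clinical AE or abnormal laboratory result makes further dosing contrary to the subject's interest. This stands as partial cover. But the best-interest and Grade 4 stops concern a subject already being dosed, and none of these provisions is a cross-over screening criterion. At entry the plan states investigator judgment as an explicit exclusion.

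*A shorter list can be deliberate.* This stands. A reader might infer that every omitted cardiac bar is an error and that the entry list should be copied over. The documents do not support that. MI, angina, NYHA class, heart block and bundle branch block are not named stops, and section 5.2.1 describes a population with few options. A bare heart-block bar would also lose the pacemaker exception in 5.4.2.

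*The window may be narrower than the ceiling.* Section 6.2.5.2 says that cross-over screening can be completed within 3 days of the end-of-treatment visit. Two MEC or FLAG-IDA cycles with the allowed delay and window end about 28 + 14 + 28 + 14 = 84 days (2.8 months) after start. Treating start as randomization, that is by month 19.8 (R = 17) or 21.7 (R = 18.9). The earliest final locks, with a 1-month lag, are months 22.2 and 23.5. If the 3-day timing binds, no such subject qualifies at the final lock. The wording is permissive, so this makes the ceiling loose and does not make it zero.

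**Conclusion.** The point holds as a minor safety alignment. One true internal conflict exists: LVEF below 45% is a mandatory stop but not a bar to starting. Two further omissions deserve correction because the drug prolongs QT: new ventricular arrhythmia and the investigator-judgment exclusion. The 5.1 pointer is imprecise; the specific list in 5.4.4 is its natural target.

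The ceiling is about 31 to 36 controls alive at the interim cut-off or 10 to 18 at the final one, and fewer by lock, under the sample-size assumptions and the assumed drop-out and lag. The share with a low LVEF or a new arrhythmia is not in the documents.

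Two stronger inferences fail. A reader might think that cross-over contaminates the primary comparison, but it opens only after a positive result and database lock, so overall survival, alpha and power are unaffected. A reader might also conclude that a scan must be required at cross-over; the documents give no rate of LVEF decline to support that, and an undetected decline remains outside this point.

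**What to change.** Add three exclusions to 5.4.4.2:

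- (a) LVEF <45% on the most recent available assessment, matching 5.4.5;
- (b) clinically relevant ventricular arrhythmia, including torsade de pointes, since randomization;
- (c) the investigator-judgment exclusion of 5.4.2 item 20, which covers recent MI, angina, heart failure and conduction disease case by case.

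In 5.1, change the pointer from Section 5.4 to Section 5.4.4.

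The triplicate ECG, physical examination and AE/SAE review already required in 6.2.5.2, with LVEF results on record, are enough to apply these. The cost is one list edit and one cross-reference, with no new procedure and no change to sample size or analysis. The downside is that a few subjects at most lose optional post-lock access.
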